The study we are proposing has the potential to influence the way treatment of PTSD and alcohol dependence is delivered across the VA Healthcare Administration (VHA) and the Department of Defense. The population we are going to study are veterans that have served in the military and may have participated in past or current military conflicts. All participants will have current Diagnostic and Statistical Manual of Mental Disorder, 4th Edition (DSM-IV) diagnoses of PTSD and alcohol dependence, two of the most common diagnoses among veterans particularly those who have experienced combat.

Currently Cognitive Processing Therapy (CPT) and CPT-C (CPT without imaginal exposure) are being rolled out nationally in a large dissemination project by the Veterans Health Administration (VHA) and the Department of Defense (DoD) as one of two gold standards for the treatment of PTSD. Unfortunately, neither CPT nor CPT-C address the needs of patients with comorbid alcohol dependence. Our study will further test a newly developed enhanced CPT-C (E-CPT-C) for veterans with PTSD and comorbid alcohol dependence. The study will test E-CPT-C in combination with a new pharmacotherapy for veterans with PTSD and alcohol dependence. Zonisamide is a promising new pharmacotherapy for alcoholism. If effective, it has the potential to be prescribed as a first line medication for alcoholism for veterans.

Overview:

This is a randomized, controlled trial with 100 veterans diagnosed with PTSD and comorbid alcohol dependence. Veterans will be randomized to receive either zonisamide (400 mg) or placebo for 12 weeks in a double blind fashion. Randomization will be done using 3:1 ratio and will be performed by our research pharmacy using a random assignment in blocks of 4- 3 will be assigned to active medication and 1 to placebo.. Medication will be titrated over a 6 week titration phase followed by a 6 week treatment phase. All veterans will receive E-CPT-C therapy for the 12 weeks of treatment; E-CPT-C will be provided by trained and qualified clinicians with extensive experience providing E-CPT-C. Veterans will be recruited primarily through advertisement, but also through the clinical facilities at the VA and from other collaborators.

Experimental subjects:

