Fifty veterans aged 21- 65 years old, with a current Diagnostic and Statistical Manual-IV, TR (DSM-IV) diagnosis of PTSD, assessed by the Structured Clinical Interview for DSM Disorders (SCID) & Clinician Administered PTSD Scale for DSM-IV (CAPS), and alcohol dependence (assessed using Structured Clinical Interview for DSM-IV) will be enrolled.

Study Procedures:

Overview: After signing informed consent, participants will undergo an initial assessments and screening. The screening will consist of careful psychiatric and medical evaluation that will also include screening for a veteran's potential to develop alcohol withdrawal. Those veterans who need treatment for alcohol withdrawal will be referred to our detoxification clinic as a first line of treatment. Initial assessments will include a careful diagnostic evaluation completed by highly trained and experienced research personnel, as well as collection of baseline assessments of alcohol use, PTSD symptoms and other characteristics. Veterans will be randomized to zonisamide 400mg or placebo for 12 weeks. The dose and titration schedule for zonisamide was selected based on data from clinical trials and is consistent with the recommended dosing schedules. All veterans will also be enrolled in E-CPT-C therapy. Assessments will occur weekly. At each visit veterans will have an interview with a member of the research staff whom is not providing the E-CPT-C training, receive a supply of medication, and complete self-report measures. Veterans will be compensated for their participation using a schedule outlined below. There will be one follow up session 3 months after completion of treatment.

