The target sample is 100 veterans diagnosed with PTSD and comorbid alcohol dependence. Veterans will be recruited from: 1) advertisement, 2) from PTSD clinics and patient units at VA Connecticut Healthcare System (VACT), and 3) from the group of patients entering treatment for alcohol use disorders at VACT Substance Abuse Treatment Program. We will review existing medical records to identify potential participants. Outreach will also be conducted to local Veteran Centers, where staff from VACT consults. The PTSD staff has also been involved in outreach to the community for returning OIF/OEF veterans. Each veteran will be carefully screened and assessed using the inclusion and exclusion criteria found above in Section 8.

X. Informed Consent Process

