Table 1. Summary of Weekly Study Assessments

Assessments	0	1	2	3	4	5	6	7	8	9	10	11	12	13	14	25
SCID I	x															
TLFB	x	x	x	x	x	x	x	x	x	x	x	x	x	x	x	x
OCDS		x	x	x	x	x	x	x	x	x	x	x	x	x	x	x

ADS	x														
Demographics	x														
CIWA	x														
CAPS Dx	x														
CAPS Sx		x		x		x		x		x		x		x	x
HAMD		x	x	x	x	x	x	x	x	x	x	x	x	x	x
PCL-C		x	x	x	x	x	x	x	x	x	x	x	x	x	x
SAFTEE		x	x	x	x	x	x	x	x	x	x	x	x	x	x
Independent Psychiatric Exam	x														
Physical Examination	x														
Medication Count		x	x	x	x	x	x	x	x	x	x	x	x	x	x
EKG	x														
Medical History	x														
Labs	x				x			x				x			x
UTOX	x	x	x	x	x	x	x	x	x	x	x	x	x	x	x

Data Analysis:

Descriptive statistics and graphs will be used to summarize the data on all randomized veterans. All continuous variables will be examined for adherence to the normal distribution using normal probability plots and Kolmogorov-Smirnov tests. Transformations will be applied if needed. If normality is not satisfied and transformations do not help with achieving normality alternative analytic strategies will be considered such as generalized estimating equations (GEE) or nonparametric methods for repeated measures analysis (Brunner et al 2002). For the primary hypotheses we will use mixed effects models to assess change in alcohol consumption and craving over time. Study medication (zonisamide vs placebo) and time (in weeks and months) will be used as a within-subject factors. The primary outcome drinking variable will be heavy drinking days and drinks per week calculated from the timeline data.

If significant differences between groups are observed Bonferroni adjusted post-hoc tests will be performed to test group differences at each time point. The same model will be used to examine changes in craving (using the OCDS) and PTSD symptoms (using the PCL every week and the CAPS every two weeks) over time.

XII. Labeling and Storage of Data and Specimens

All data and blood specimens will be stored without direct identifiable information, but will be identifiable via a linking code. Blood will not be used for the purpose of establishing cell lines. Any hard copy records associated with the study will be kept in locked offices. The secured research records are labeled with code numbers only (names and other identifying information are kept separate from research records). Access to hard copy data is only given to

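### The protocol gives two enrolment totals, 100 and fifty veterans, and nothing in it says which one governs.

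*Combined protocol and SAP*

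**What the plan says.** Three places in the current text state the size of the trial.

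- Section VII, Overview: "This is a randomized, controlled trial with 100 veterans diagnosed with PTSD and comorbid alcohol dependence".
- Section VII, Experimental subjects, directly after the Overview: "Fifty veterans aged 21- 65 years old, with a current Diagnostic and Statistical Manual-IV, TR (DSM-IV) diagnosis of PTSD". The sentence ends "alcohol dependence (assessed using Structured Clinical Interview for DSM-IV) will be enrolled".
- Section IX, Subject Recruitment and Screening: "The target sample is 100 veterans diagnosed with PTSD and comorbid alcohol dependence".

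The Overview also fixes the allocation: "Randomization will be done using 3:1 ratio", by "random assignment in blocks of 4- 3 will be assigned to active medication and 1 to placebo".

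The protocol contains no sample-size or power justification. It states no significance level, target effect, outcome SD or dropout rate, and no rule for ending enrolment.

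**The concern.** All three statements describe the same population, and the totals differ by a factor of two. With no calculation behind either figure, the stated number is the only definition of the trial's size, and it is stated two ways.

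As written, the protocol would support closing enrolment at 50 or at 100. That affects the precision of every zonisamide versus placebo comparison, and most of all the size of the smaller placebo arm. It also leaves open whether the stopping point was set in advance. A single stated number removes that question.

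**Working it through.** **Inputs from the protocol.** Total N of 100 (section VII, Overview; section IX) or 50 (section VII, Experimental subjects). Allocation 3:1 in blocks of 4 (section VII, Overview). Neither total can be reproduced from a calculation, because the protocol gives none.

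**Step 1: can the figures be reconciled?**

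- Fifty as an arm: 100 × 3/4 = 75 and 100 × 1/4 = 25. Neither is 50.
- Fifty randomized out of 100 recruited: the Overview gives 100 as the size of the randomized trial itself, and the other sentence says the fifty are to be enrolled.
- Fifty as completers or as a first stage: no section says so, and no dropout assumption or staged design appears.

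**Step 2: arms and blocks.**

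- N = 100: 100/4 = 25 complete blocks, giving 75:25.
- N = 50: 12 complete blocks (36:12) plus 2 veterans from the 13th. Those two are either both active (38:12) or one of each (37:13).

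A trial can stop part-way through a block, so this only mildly favours 100.

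**Step 3: precision.** For a common outcome SD, the approximate 95% half-width in SD units is 1.96 × √(1/n₁ + 1/n₂).

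| Arms | Calculation | Half-width | Ratio to 75:25 |
|---|---|---|---|
| 75:25 | 1.96 × √(1/75 + 1/25) | 0.453 | 1 |
| 37:13 | 1.96 × √(1/37 + 1/13) | 0.632 | 1.396 |
| 38:12 | 1.96 × √(1/38 + 1/12) | 0.649 | 1.434 |

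The ratios depend only on the arm sizes. With t quantiles in place of 1.96 the half-widths are 0.458, 0.648 and 0.666, and the ratios 1.41 to 1.45.

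**Step 4: illustration on assumed design values.** Assume a two-sample t-test at one endpoint, two-sided alpha 0.05 and no dropout. None of these is stated in the protocol. Power is computed from the noncentral t distribution with noncentrality d/√(1/n₁ + 1/n₂) and n₁ + n₂ − 2 degrees of freedom.

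| Arms | Difference detectable with 80% power | Power at 0.65 SD |
|---|---|---|
| 75:25 | 0.653 SD | 0.796 |
| 37:13 | 0.922 SD | 0.506 |
| 38:12 | 0.947 SD | 0.486 |

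**Step 5: sensitivity of the 80%-power difference to the assumptions.**

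- Averaging 12 equally correlated weekly values multiplies it by √((1 + 11ρ)/12). For ρ from 0.4 to 0.8 it becomes 0.44 to 0.59 SD at N = 100, against 0.62 to 0.86 SD at N = 50.
- Losing 20% to 40% of each arm, without repeated measures, gives 0.73 to 0.85 SD against 1.04 to 1.24 SD.

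The absolute values move with the assumptions. The ratio between the two readings stays at 1.41 to 1.46.

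**The case against.** The best defence is that the number is contradictory rather than missing, with one outlier. The figure of 100 appears twice, in the design overview and, as the target, in the recruitment section. Fifty appears once, in a sentence that is mainly about diagnosis and may be left over from an older text. A reader would probably settle on 100. The protocol also calls the study a pilot in several places and makes no power claim that N = 50 would falsify.

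The first part stands as evidence about intention, and it is why 100 is the more coherent correction. It does not remove the conflict. No section says that fifty is superseded, and the pilot label makes fifty a plausible total.

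Two further points are fair. The detectable differences and powers rest on assumptions that the protocol does not supply, and the 0.65 SD benchmark is itself roughly what 100 veterans can detect with 80% power, so those figures only show the consequence of halving the trial. And the protocol does not define enrolled as consented or as randomized, although consent precedes screening. That does not explain fifty, but the correction should settle it.

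**Conclusion.** The concern holds. The protocol states two incompatible totals for the same trial and gives no rule for choosing between them, so when enrolment is complete is not uniquely fixed. This is a basic design figure and must be corrected.

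Without any outside assumption, the conflict is 100 against 50 in total and a placebo arm of 25 against 12 or 13. With the sole assumption of a common outcome SD, interval widths differ by a factor of about 1.4. On the illustrative t-test assumptions, the detectable difference is about 0.65 SD against 0.92 to 0.95 SD. None of this shows which total was intended or that either is adequate.

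**What to change.** Reconcile the Overview and Experimental subjects paragraphs of section VII with section IX, so that all three give one fixed total. Say that it counts randomized veterans, and add the expected arm sizes.

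- If 100 is the target, change fifty to 100 in the Experimental subjects paragraph and state 75 zonisamide and 25 placebo, in 25 blocks of 4. This is the most coherent correction, chiefly because 100 is stated twice, once as the target; it also fits the blocks exactly.
- If 50 is the target, correct the Overview and section IX, and state that the expected arms are 37:13 or 38:12.

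If a detectable difference is added, it should come from the sponsor's own planned mixed-effects analysis and dropout assumption, not from the illustration here. The cost of the reconciliation is wording only.

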Initial Assessments/Screening: In order to qualify for participation, veterans will complete the following: (1) Diagnostic interview with the Structured Clinical Interview for DSM Disorders (SCID I), a comprehensive psychiatric interview schedule designed to assess psychiatric disorders in adults (First et al 1996). The SCID interview schedule covers the major Axis I psychiatric disorders defined in DSM-IV. The SCID permits comprehensive assessment of substance use as well as comorbid psychiatric disorders. (2) Drinking patterns will be assessed using The TLFB method (Sobell and Sobell 1992). This will allow documentation of the degree and frequency of daily alcohol consumption and smoking pattern. (3) PTSD symptom will be assessed using the Clinician Administered PTSD Assessment (CAPS), and (4) Veterans will have a medical history and physical examination by one of the investigators, blood tests (including SMAC-20, serum gamma-glutamyl transferase (γ -GGT), CBC with differential, thyroid function tests, and TSH), urinalysis, urine toxicology, and an electrocardiogram (EKG). It is anticipated, however, that

mild to moderate elevations in liver function tests will be common in alcohol dependent subjects. Veterans with LFT abnormalities that do not exceed 3 times normal values will be included.

Study Treatments:

Medication Treatment: Zonisamide, (target 400 mg) will be titrated upward over 6 weeks. Dosing will be given once daily and veterans on placebo will be given identical number, color and consistency of capsules as those on active medication. Below is the proposed dosing schedule, although we will make adjustments if side effects occur:

Zonisamide 400mg/day

Week 1:	Days 1-7	ZON 100mg, +	= TOTAL 100mg
Week 2:	Days 1-7	ZON 200mg, +	= TOTAL 200mg
Week 3:	Days 1-7	ZON 200mg, +	= TOTAL 200 mg
Week 4:	Days 1-7	ZON 300mg, +	= TOTAL 300 mg
Week 5:	Days 1-7	ZON 300mg, +	= TOTAL 300 mg
Week 6:	Days 1-7	ZON 400mg, +	= TOTAL 400 mg
Week 7-12:	Days 1-42	ZON 400mg, +	= TOTAL 400 mg

Week 13-14: TAPER by 100 mg every 3 days for a total of 2 weeks.

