Pharmacy Procedures: Veterans will start study medication on the day of randomization. The authorized prescribers of zonisamide for the study are [name]., [name]., [name]., [name] and [name]. The research pharmacy will dispense the medications and will take back any medications that are not used, keeping a record of used and unused medications. In addition to that we will record at each visit that the medication was dispensed, the number of pills, and if any medications were missed during the previous week. The study nurse will administer the first dose and veterans will be asked to stay in the research office for approximately 1 hour after the dose is administered. The zonisamide will be started at a low dose (see schedule above) and titrated upward based on the outlined schedule. The target dose for the zonisamide will be 400mg/day. Veterans will meet with the study nurse every visit to discuss any side effects of the medications, and will do study assessments with the research personnel. If veterans experience side effects that cannot be managed by adjustments in the timing of the medication (i.e. taking at bedtime, etc.), veterans may have their medication titration either held or the medication dose may be decreased. The study psychiatrist (who is blinded to the condition, but may request a dose decrease to the next lowest dose) and the research pharmacist (who is not blinded, but who has no contact with the veteran) will do this. The psychiatrist will contact the pharmacist and request a decrease in dose. In case of an emergency, the blind will be broken and appropriate medical care initiated. Since this is a pilot study, the proposed dosing schedule will be evaluated and may be modified depending on the findings from the pilot study.

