Initial assessment will include the following measures: (1) Alcohol Dependence Scale (ADS) (Skinner and Allen 1982) is a self-report measure of alcohol dependence consisting of 25 items and will be used to measure the degree of dependence and control for possible group differences in alcohol dependence. (2) Clinical Institute Withdrawal Assessment Scale (CIWA, Ar) (Sullivan et al 1989) is an interviewer driven measure of alcohol withdrawal consisting of 10 items rated on a scale from 0 to 7 and will be used to rule out withdrawal symptoms requiring medical treatment. (3) Demographic information will be collected including contact information and self-designated racial and ethnic data, in accordance with National Institute of Health guidelines.

Study Assessments will include the following: (all measures – except the CAPS which will be used every two weeks - will be administered on each study visit, every week).

(a) The Timeline Follow-Back (TLFB) method (Sobell and Sobell 1992) will be used to document the degree of daily alcohol consumption and to monitor the use of other substances during 12 weeks of treatment.

(b) Obsessive-Compulsive Drinking Scale (OCDS) (Anton et al 1995) will be used to measure alcohol craving throughout the study. The OCDS consists of two subscales and measures obsessive and compulsive thoughts related to drinking.

(c) Clinicians Administered PTSD Scale (CAPS) will be used to obtain data on the frequency and severity of PTSD symptoms and will be administered every two weeks.

(d) Hamilton Depression Scale (HAMD) (Hamilton 1960) will be used to assess the degree and severity of depressive symptomatology. Given the overlap of PTSD and depression this scale will serve as another measure of psychiatric symptomatology.

(e) Posttraumatic Stress Disorder Checklist (PCL-C) will be used to measure PTSD symptoms every week on each visit. The PCL-C is a self-report scale that shares similar

reliability with the CAPS. (Weathers et al 1996)

(f) Modified Version of the Systematic Assessment for Treatment Emergent Events (SAFTEE) will be used to collect information on emergent side effects and their severity (weeks 1-12). This modified version will include, among other side effects, symptoms associated with zonisamide including: fatigue, decreased appetite, dizziness, headache, nausea, and agitation/irritability.

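### No craving score (OCDS) is scheduled before the first dose, although hypothesis 1c concerns a reduction in craving

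*Combined protocol and SAP*

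**What the plan says.** Craving on the OCDS is hypothesis 1c under Specific Primary Aim 1 (Section VII, Research Objectives). Section XI, Data Analysis, says: "For the primary hypotheses we will use mixed effects models to assess change in alcohol consumption and craving over time". It names neither a baseline time point nor a baseline covariate.

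On timing, Section XI, Study Assessments, item (b) says the OCDS "will be used to measure alcohol craving throughout the study". The sentence introducing that list says all measures except the CAPS "will be administered on each study visit, every week". The Study Procedures overview in Section VII adds that at each visit veterans "receive a supply of medication, and complete self-report measures". The table headed "Table 1. Summary of Weekly Study Assessments" leaves the OCDS blank at week 0 and marks it at weeks 1 to 14 and 25. The timeline follow-back (TLFB) is marked at week 0.

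On dosing, Section VII, Pharmacy Procedures, says: "Veterans will start study medication on the day of randomization". It continues: "The study nurse will administer the first dose and veterans will be asked to stay in the research office". It does not say whether questionnaires come before or after that dose.

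**The concern.** A hypothesis about reducing craving, tested by a model of change over time, would normally start from a score taken before treatment. As scheduled, the first OCDS appears to come after about a week of study drug. Any effect present by then is absorbed into the first measurement. The plan does not say which model term tests 1c. If it is the treatment-by-time term, an early effect is partly hidden. If it is the overall difference between arms, a chance imbalance in craving can be neither seen nor adjusted for.

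The plan itself values baseline control: it collects the Alcohol Dependence Scale (ADS) partly to allow for group differences in dependence. Drinking has a week-0 TLFB and PTSD has a week-0 CAPS. Craving is the only Aim 1 outcome with no scheduled pre-dose value, and a missed pre-dose score cannot be recovered later.

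**Working it through.** The plan gives no sample-size calculation, OCDS standard deviation or effect size, so there is no figure of its own to reproduce.

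**1. Table 1.** The header has 16 columns (weeks 0 to 14, and 25). The TLFB row has 16 marks. The OCDS row has 16 cells, the first blank, and 15 marks. Both rows are complete, so the blank is not an extraction fault. The rows after the page break have lost a column.

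**2. Lists of initial measures.** The Section VII list, which opens "In order to qualify for participation, veterans will complete the following", names the SCID, TLFB and CAPS. The Section XI list names the ADS, CIWA and demographics. Together these are the six interview or questionnaire rows marked at week 0. The OCDS is in neither list.

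**3. Is week 1 after the first dose?** No passage says so outright. Four points indicate it:
- Medication starts on the day of randomization with a nurse-given dose.
- Medication counts start at week 1, and Medication Adherence describes them as counts of left-over medication.
- Section XV pays for baseline separately. With 11 weekly visits, 20 + 30 + 11×30 + 50 + 30 + 30 + 30 = $520, the stated total. Merging baseline with week 1 gives 20 + 30 + 10×30 + 50 + 30 + 30 + 30 = $490.
- Follow-up is 3 months after treatment ends and is labelled week 25. Since 25 − 12 = 13 weeks, or about 3.0 months, week numbers appear to count elapsed time.

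**4. Chance imbalance at baseline.** Inputs: 3:1 allocation and a total of 100 (Sections VII Overview and IX), or fifty (Section VII, Experimental subjects). The 0.25 SD threshold is chosen for illustration.
- N = 100: SE = √(1/75 + 1/25) = 0.231 SD; P(|difference| > 0.25 SD) = 2[1 − Φ(0.25/0.231)] = 0.28.
- N = 50: SE = √(1/37.5 + 1/12.5) = 0.327 SD; probability = 0.44.

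**5. Precision forgone (illustrative).** For a single post-treatment OCDS, adjusting for a baseline score with correlation r to follow-up multiplies residual variance by 1 − r². The detectable difference is (1.960 + 0.842) × SE × √(1 − r²), assuming two-sided 5% and 80% power.

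| Assumed r | Variance reduction | Detectable, N = 100 | Power at 0.5 SD, N = 100 | Detectable, N = 50 | Power at 0.5 SD, N = 50 |
|---|---|---|---|---|---|
| no baseline | – | 0.65 SD | 58% | 0.92 SD | 33% |
| 0.3 | 9% | 0.62 SD | 62% | 0.87 SD | 36% |
| 0.5 | 25% | 0.56 SD | 71% | 0.79 SD | 42% |
| 0.7 | 49% | 0.46 SD | 86% | 0.65 SD | 57% |

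**6. Allowing for ADS or TLFB as covariates.** Suppose such a covariate correlates 0.3 with follow-up OCDS and 0.4 with baseline OCDS. Then R² = (r² + 0.09 − 2·r·0.3·0.4)/(1 − 0.16), and the further reduction is 1 − (1 − R²)/(1 − 0.09). For r = 0.3, 0.5 and 0.7 this gives 4%, 19% and 44%.

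**The case against.** The strongest reply is that the text can be read to include a baseline OCDS. The first dose is given at a visit, and the text calls for self-report measures at each visit. Table 1 is only a summary: it has 16 columns for 17 paid appointments (screening, baseline, 11 weekly, weeks 12, 13 and 14, follow-up) and no row for urinary ethyl glucuronide (EtG), although the text uses baseline EtG values. An unlisted pre-dose OCDS therefore cannot be excluded. The payment total shows only that baseline is separate from the weekly visits, not on which of them dosing begins, and a medication count could in principle record dispensing. These limits stand. But neither general sentence places the form before the dose, and staff following Table 1 would not give it at week 0.

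It is also fair that the stated primary drinking variables, heavy drinking days and drinks per week, both come from the TLFB, which has a week-0 value. Randomization protects the on-treatment OCDS comparison, and its standard error already allows for chance imbalance. Week 1 is the lowest step of the titration, so change from week 1 onward remains estimable. The 28% would apply to any unmeasured trait in a 75:25 trial, and the precision figures rest on assumed correlations and a single comparison rather than the planned repeated-measures model. These points limit the harm. They do not supply a pre-treatment value.

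**Conclusion.** The concern holds: the plan schedules no OCDS before the first dose for hypothesis 1c. That week 1 is post-dose is a well-supported inference, not a stated fact. The between-arm comparison of on-treatment craving is not invalidated. The losses are change from pre-treatment craving, any check of baseline balance in craving with about 25 veterans on placebo, and some precision. The chance of an unseen imbalance above 0.25 SD is 28% (44% at N = 50). The variance reduction forgone is 9% to 49% with no other covariate, or 4% to 44% beyond an ADS or TLFB covariate, over assumed baseline correlations of 0.3 to 0.7. The change is cheap and worth making, even if the team already intends a baseline form.

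Secondarily, the PCL-C, HAMD and SAFTEE are also blank in their first cell. Their rows lost a column, but the ADS, CIWA and EKG rows are marked in that same cell, so it is week 0. This matters less. PTSD has a week-0 CAPS, and the drug-placebo contrast in side effects is valid without a baseline, although an individual complaint cannot then be judged new or worse on the same scale.

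**What to change.** - Mark the OCDS at week 0 in Table 1.
- State in Section XI that it is completed before the first dose, and reconcile this with the sentence about administration at each study visit.
- In Data Analysis, name the pre-dose OCDS as the baseline covariate in the mixed model for 1c, and report it by arm.
- Secondarily, mark the PCL-C, HAMD and SAFTEE at week 0, and call an individual side effect treatment-emergent only if it is new or worse than at week 0.

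The main change costs one short form at a visit that already takes place, a table edit and one sentence in the analysis section. The secondary change adds a few more short forms at the same visit.
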